### **E2. Subjects**

Gender:

Both

Age:

Adult (18-64 yrs)

Ethnicity:

All Ethnicities

Primary Language:

English

Groups to be recruited will include:

Asymptomatic patients with chronic conditions, healthy

Which if any of the following vulnerable populations will be recruited as subjects?

Mentally ill

Vulnerable populations require special protections. How will you obtain informed consent, protect subject confidentiality, and prevent undue coercion?

We will recruit male and female Veterans with mild to moderate symptoms of anxiety and depression. Participants who have poorly controlled mental illness that prevent capacity to provide consent will be excluded from the study. Participants who are unable to provide informed consent or who demonstrate cognitive limitations as evidenced by a score of 3> on a cognitive screen will be excluded from the study. We will use the teach back method of ensuring the Veteran understands the purpose, procedures, benefits and risks of participation of the study to ensure they understand, are able to provide proper consent and to prevent any coercion. Veterans who are unable to successfully repeat back the study information will be excluded. We will also consent individuals after they have discharged from the hospital and have been back in their home setting to prevent obtaining consent from anyone under duress associated with an acute care setting.

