In Phase II: The PI will pilot IM Whole by treating 5 Veterans suffering from stroke and comorbid psychological distress. Five Veterans with stroke and comorbid psychological distress will be recruited from the stroke acute care unit, rehabilitation unit, and outpatient stroke follow-up clinic. Qualitative interviews asking the Veterans opinion regarding the treatment content and delivery method will be administered at the end of the final session.

In phase III: Interested Veterans will be randomized to IM Whole (n=15) or usual care plus education (UC+E) (n=15), respectively. Veterans in the UC+E group will receive standard acute care, rehabilitation unit or

outpatient follow-up clinic stroke treatment provided at the MEDVAMC. The standard of care for these patients consists of appointments in the outpatient stroke follow-up clinic, medication management for comorbid chronic diseases, and general physical rehabilitation exercises. To account for additional treatment contact provided to participants in I'm Whole, UC+E will also receive 6 brief telephone calls with information regarding unrelated health topics (e.g., breast, colon, rectal, esophageal, skin and testicular cancer treatment and prevention). We will track the number of patients screened, number and percent of patients eligible, number randomized, number and percent completing treatments, and number and percent completing subsequent follow-up assessments following treatment completion. Veterans in I'm Whole will complete the same qualitative interviews described in phase II.

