**Inclusion Criteria:**

Inclusion for Phase II and Phase III: 1) a documented history of stroke and/or transient ischemic attack within the last 30 days, 2) a modified Rankin score of > 3, 3) regular access to a computer or tablet with internet and a camera, 4) ability to give appropriate informed consent, 5) score > 5 on a measure of depression (Patient Health Questionnaire [PHQ-8]) and/or >17 on a measure of anxiety (Generalized Anxiety Disorder-7 [GAD-7]) assessments, 6) ability to ambulate with or without assistance of a cane or walker.

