**Exclusion Criteria:**

Exclusion Criteria for Phase II and Phase III: 1) cognitive impairment, as evidenced by a score of >3 on a brief cognitive screener; 2) documented diagnosis of psychotic disorder or schizophrenia; 3) documented severe depression, anxiety (based on PHQ-8 or GAD-7 score of > 20), or hospitalization for psychiatric illness within the past 30 days.

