Phase II and Phase III: Screening and Recruitment Procedures. We will recruit men and women Veteran stroke patients of all races and ethnicities with depression and anxiety symptoms who are being treated in the stroke acute care inpatient unit, rehabilitation unit, or outpatient stroke follow-up clinic at the Michael E. DeBakey VA Medical Center (MEDVAMC). The MEDVAMC treats over 310 Veterans with stroke each year, of which approximately 93 (33%) have comorbid psychological distress. We have successfully recruited Veteran stroke patients in our previous stroke studies. The research assistant (RA) will approach potential participants at bedside in the acute or rehabilitation unit or during the first follow-up visit after admission from the stroke acute care unit. Veterans interested in the study will be screened for eligibility via their electronic medical records (EMR) to see if they meet preliminary study inclusion/exclusion criteria (listed above). Those who meet the eligibility criteria will receive a follow up session, in their home or at the MEDVAMC to be administered the screening measurements listed above. If participants via EMR review or baseline assessments: 1) do not demonstrate or show evidence of a cognitive impairment, as evidenced by a score of >3 on a brief cognitive screener; 2) have a documented diagnosis of psychotic disorder or schizophrenia; 3) score in the severe range for depression, or anxiety (based on PHQ-8 or GAD-7 score of > 20), or have a documented or self-reported hospitalization for psychiatric illness within the past 30 days, they will be invited to participate in the study. They will be provided instructions regarding using VTEL to conduct their sessions, given a *I'm Whole* workbook and scheduled a time for first session with the study clinician. A note will be placed in the electronic medical records (EMR)s documenting the visit. Participants who do not meet the criteria will be immediately notified of their ineligibility. A note will be placed in the EMR documenting why they were not eligible. Their primary care provider will be signed to the note for follow up discussion regarding possible referrals or additional services needed for the Veteran. The Veteran will also be provided a list of community based psychiatric and medical resources.

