## **Section R: Advertisements**

### **Mode of Advertising: Billboard**

Exact language of Advertisement:

People who have had a stroke often experience sadness and worry. Untreated or poorly managed sadness and/or worry can cause poor progress after having a stroke and cause people to spend less time exercising or being with their family and friends.

The overall goal of this program is to develop, refine, and see if the I'm Whole treatment for Veterans with stroke and sadness and worry helps improve your way of living.

If you have had a stroke in the past year and have sadness and/or worry and would like to receive additional strategies to help you perform better physically and socially then I'm Whole can help. If you are interested in hearing more about the program please contact:

[name] Principal Investigator [name] [name]

Thank you for your time and welcome to the I'm Whole program!

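### The eligibility text contradicts itself: the screening procedure reverses the exclusions, the advertisement uses a different stroke window, and the anxiety-alone entry route is narrow and unexplained

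*Combined protocol and SAP*

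**What the plan says.** All references are to the combined protocol and SAP.

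- **F1, Inclusion Criteria.** Stroke or TIA must fall within 30 days. Item 5 requires PHQ-8 above 5 "and/or >17 on a measure of anxiety (Generalized Anxiety Disorder-7 [GAD-7]) assessments".
- **F1, Exclusion Criteria.** Veterans are excluded for cognitive impairment (screener score above 3), for psychotic disorder or schizophrenia, for severe depression or anxiety ("based on PHQ-8 or GAD-7 score of > 20"), and for psychiatric hospitalization in the preceding 30 days.
- **F2, screening and recruitment.** A numbered list gives the findings that lead to an invitation. Item 1 is the absence of cognitive impairment. The list continues with Veterans who "have a documented diagnosis of psychotic disorder or schizophrenia; 3) score in the severe range for depression, or anxiety" (same cut-off of 20), or who had a recent psychiatric hospitalization, and ends "they will be invited to participate in the study".
- **J1, Waiver of Consent.** The programme is described as unsuitable for people in severe distress.
- **E2, Subjects.** "We will recruit male and female Veterans with mild to moderate symptoms of anxiety and depression". The cognitive cut-off is printed as 3>, where the Exclusion Criteria and F2 print >3.
- **Section R, advertisement.** It addresses people whose stroke was within a year and who have sadness, worry or both.
- **F1, Design.** The quantities to be tracked include the number screened and the "number and percent of patients eligible".

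**The concern.** Screening staff work from F2, and F2 as written invites people whom F1 excludes. Potential participants see the advertisement, and it reaches people whom F1 cannot accept. Item 5 combined with the severe-score exclusion also leaves Veterans whose only qualifying symptom is anxiety a very small range of admissible scores, immediately below the exclusion cut-off, with no reason given.

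What is at stake is who enters a small pilot (5 in phase II, 30 in phase III) and the meaning of the eligibility percentage that the pilot is meant to report.

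**Working it through.** **1. F2 against the Exclusion Criteria.** In F2 the negation stands inside item 1, after its number. Items 2 and 3 have none. Taking each item literally:

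- Cognitive screener above 3: not invited under F2, excluded under F1. These agree.
- Psychotic disorder or schizophrenia: a condition for invitation under F2, excluded under F1. Opposite.
- PHQ-8 or GAD-7 above 20: a condition for invitation under F2, excluded under F1. Opposite.
- Psychiatric hospitalization within 30 days: a condition for invitation under F2, excluded under F1. Opposite.

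So three of the four conditions are reversed. If the F2 items are joined by *and*, only Veterans with excluded conditions would be invited. If they are joined by *or*, such Veterans would be invited along with others. Neither reading agrees with F1 or with the J1 statement about severe distress. Carrying the negation through all items restores agreement, which suggests a drafting slip.

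**2. Stroke window.** The advertisement covers about 365 days and the inclusion criterion 30, so respondents in the remaining 365 − 30 = 335 days are addressed but ineligible. These are days, not Veterans. Let E be the number eligible and S the number screened from other sources. Adding A respondents beyond 30 days to the screening count changes the percentage from 100 × E/S to 100 × E/(S + A). The documents give no value for A and do not say at what point a respondent counts as screened.

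**3. Anxiety-alone route.** Inputs are the entry thresholds (PHQ-8 above 5, GAD-7 above 17; Inclusion Criteria) and the exclusion cut-off (above 20 on either; Exclusion Criteria). Whole-number scores are assumed. When PHQ-8 does not meet its threshold, entry needs GAD-7 above 17 and not above 20.

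- As printed: GAD-7 of 18, 19 or 20, so 20 − 17 = 3 scores.
- Entry sign read as at least, exclusion as printed: 17 to 20, 4 scores.
- Entry as printed, exclusion read as at least: 18 and 19, 2 scores.
- Both read as at least: 17 to 19, 3 scores.

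The PHQ-8 route as printed is 6 to 20, so 20 − 5 = 15 scores (14 to 16 under the other readings), and on it any GAD-7 score not above 20 is accepted. The same exclusion number thus lies 3 points above one entry threshold and 15 above the other. No section gives a reason.

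**4. Cognitive screener.** The Exclusion Criteria tie a score above 3 to impairment, and F2 repeats that sign. E2 alone reverses the symbol, while its sentence still describes limitations that lead to exclusion.

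**The case against.** **The F2 wording is obviously a slip.** Probably so. The same paragraph has already sent staff to the criteria listed earlier, and J1 makes the intention plain. A reader might infer that the study will in fact enrol Veterans with psychosis or severe distress; the documents do not support that. What stands is that the operative screening paragraph states the opposite of the exclusions.

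**The advertisement only asks interested people to make contact.** Fair. Screening follows, recruitment is mainly by bedside approach, clinic contact and referral, and F2 provides for notifying and referring ineligible Veterans. The two windows still differ.

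**Scores of 18 to 20 do not conflict with the stated population.** This stands. A reader might infer that an anxiety-alone entrant cannot have mild to moderate symptoms. The only severity cut-off in the documents is above 20, so 18 to 20 is non-severe by the plan's own rule, and mild and moderate bands are not defined. E2 also describes the two conditions jointly, as do F2 ("stroke patients of all races and ethnicities with depression and anxiety symptoms") and part of the advertisement ("Veterans with stroke and sadness and worry helps improve your way of living"). Mild or moderate anxiety can enter alongside PHQ-8 of 6 to 20, and a higher bar for anxiety alone may be deliberate. What remains is that the *and/or* in item 5, echoed in the advertisement, opens an anxiety-alone route whose narrowness is unexplained.

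**The cognitive screener has no scoring direction.** A reader might infer this from the mismatched signs. It does not hold, because the Exclusion Criteria already indicate that scores above 3 mean impairment.

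**Conclusion.** The concern holds as a set of inconsistencies in the eligibility text, in this order of weight:

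- F2 literally reverses three of the four exclusion conditions. This is a real contradiction, probably a drafting slip.
- The advertisement and the inclusion criterion give different stroke windows. This is a real mismatch that could lower the tracked percent eligible.
- The anxiety-alone window of 3 scores (2 to 4) is an unexplained asymmetry that needs confirmation. It is not a demonstrated error.
- The sign in E2 is a minor correction.

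A reader might also infer bias in the treatment comparison. The documents do not support that, since the same criteria apply to both arms before randomization. The number of Veterans affected cannot be estimated: Section C gives depression at 33% and anxiety at 24% without their overlap, and the 93 distressed Veterans a year in F2 are not split by condition or score. The score counts assume whole-number scores and say nothing about how many Veterans have each score.

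**What to change.** In one amendment:

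- Rewrite the F2 invitation sentence so that it agrees with the Exclusion Criteria, and check the telephone screening script mentioned in J1a against the corrected text.
- Align the stroke window in the Section R advertisement with that in the Inclusion Criteria.
- Have the sponsor confirm that the GAD-7 entry threshold and the *and/or* in item 5 are as intended. If they are, add a sentence of rationale. If not, reconcile E2, the Inclusion Criteria and the Exclusion Criteria. No cut-off is proposed here.
- Make the sign in E2 match the Exclusion Criteria and F2.

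The cost is eligibility, screening and advertisement wording only, with no added procedures.

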**Exclusion Criteria:**

Exclusion Criteria for Phase II and Phase III: 1) cognitive impairment, as evidenced by a score of >3 on a brief cognitive screener; 2) documented diagnosis of psychotic disorder or schizophrenia; 3) documented severe depression, anxiety (based on PHQ-8 or GAD-7 score of > 20), or hospitalization for psychiatric illness within the past 30 days.

## **F2. Procedure**

Phase I: The PI will merge stroke self-management and psychological distress treatment modules from their established EPiC and VSTOP-II programs. The first module will combine the VSTOP-II stroke self-management education regarding stroke risk factors and EPiC psychoeducation on how comorbid psychological distress can create barriers to engaging in stroke self-management behaviors. Clinicians will work with each Veteran to establish individualized plans for psychological distress management and strategies for practicing tailored PF, physical activity and SRF behaviors in line with the Veteran's values. Progress towards the Veteran's tailored PF, physical activity and SRF behaviors will be reviewed, and psychological distress barriers will be discussed in future modules. Modules 2-5 will be electives that provide CBT-based behavioral activation, social-support, cognitive-restructuring, thought-stopping, deep-breathing, and problem-solving skills for improving psychological distress-related barriers to practicing established PF, physical activity and SRF behaviors. Module 6 consists of a relapse prevention plan for continued management of psychological distress. Homework and tracking logs will be provided at the end of each session. [name] will provide feedback during the development and refinement stages regarding creating tailored PF and physical activity strategies for participants. [name] will provide feedback in the development and refinement stages regarding client-centered strategies for reintegrating into family and community roles and activities poststroke. The treatment will consist of 6 sessions over 6 weeks and will be delivered to Veterans in their homes, using VT technology. A clinician manual and patient workbook will be developed. There will be no Veteran involvement at this phase.

In Phase II: The PI will pilot I'm Whole by treating 5 Veterans suffering from stroke and comorbid psychological distress. Five Veterans with stroke and comorbid psychological distress will be recruited from the stroke acute care unit, rehabilitation unit, and outpatient stroke follow-up clinic. The participants will receive each of the I'm Whole sessions using VT in the home. Sessions will be delivered weekly over 6 weeks. Clinicians will work with the Veteran to establish goals in the first session that will be reviewed through the remaining sessions. Qualitative interviews asking the Veterans opinion regarding the treatment content and delivery method will be administered at the end of the final session.

The barriers to receiving the intervention via VT and acceptability of the intervention content and procedures will be assessed informally after each session, and responses will be reviewed at weekly team meetings to address any unanticipated results and make needed immediate changes to the intervention. A semi-structured interview will occur with each Veteran post-treatment, conducted by the RA trained by Co-I [name], an expert in qualitative methods. Interviews will occur by phone and include open-ended questions regarding recruitment; engagement and retention strategies; assessment procedures; participant burden; redundancy and length and frequency of treatment; effectiveness, usefulness of I'm Whole content, and perceived benefits and barriers to receiving the sessions via VT to the Veteran's home. Detailed notes will be taken during interviews, which will also be audio recorded and transcribed for analysis. Rapid analysis is a systematic and rigorous process of condensing qualitative data to quickly identify key findings to inform study progress (i.e., refine and modify I'm Whole content, delivery methods and treatment procedures). The information from the transcribed notes and feedback received in weekly meetings will be used to modify the IM WHOLE treatment.

Phase II and Phase III: Screening and Recruitment Procedures. We will recruit men and women Veteran stroke patients of all races and ethnicities with depression and anxiety symptoms who are being treated in the stroke acute care inpatient unit, rehabilitation unit, or outpatient stroke follow-up clinic at the Michael E. DeBakey VA Medical Center (MEDVAMC). The MEDVAMC treats over 310 Veterans with stroke each year, of which approximately 93 (33%) have comorbid psychological distress. We have successfully recruited Veteran stroke patients in our previous stroke studies. The research assistant (RA) will approach potential participants at bedside in the acute or rehabilitation unit or during the first follow-up visit after admission from the stroke acute care unit. Veterans interested in the study will be screened for eligibility via their electronic medical records (EMR) to see if they meet preliminary study inclusion/exclusion criteria (listed above). Those who meet the eligibility criteria will receive a follow up session, in their home or at the MEDVAMC to be administered the screening measurements listed above. If participants via EMR review or baseline assessments: 1) do not demonstrate or show evidence of a cognitive impairment, as evidenced by a score of >3 on a brief cognitive screener; 2) have a documented diagnosis of psychotic disorder or schizophrenia; 3) score in the severe range for depression, or anxiety (based on PHQ-8 or GAD-7 score of > 20), or have a documented or self-reported hospitalization for psychiatric illness within the past 30 days, they will be invited to participate in the study. They will be provided instructions regarding using VTEL to conduct their sessions, given a *I'm Whole* workbook and scheduled a time for first session with the study clinician. A note will be placed in the electronic medical records (EMR)s documenting the visit. Participants who do not meet the criteria will be immediately notified of their ineligibility. A note will be placed in the EMR documenting why they were not eligible. Their primary care provider will be signed to the note for follow up discussion regarding possible referrals or additional services needed for the Veteran. The Veteran will also be provided a list of community based psychiatric and medical resources.

Phase II and Phase III: Treatment Procedures and Development-- Sessions will be conducted by 1 clinician with master's-level training in health education, counseling or social work and expertise in CBT, psychological distress treatment, and/or chronic disease management. The clinician will conduct the sessions from the MEDVAMC using VA Video Connect VT to the Veterans in their homes. The MEDVAMC frequently uses VT for clinical treatment and research and has established VT programs and equipment that is VHA approved and readily available.

Assessment Procedures. Each participant in phase II and phase III will receive \$20.00 for each assessment they complete (0/6/12 weeks). Assessments will be conducted by an Independent Evaluator (IE). We estimate that each assessment will take about 30 to 40 minutes. If scores on the psychological distress measure worsen (e.g., 20% or more increase), the PI will be notified and participants referred to mental health treatment within the MEDVAMC or the community.

Phase III: This group will consist of the treatment (*I'm Whole* group) and usual care group will receive the standard of care. The standard of care for these patients consists of appointments in the outpatient stroke follow-up clinic, medication management for comorbid chronic diseases, and general physical rehabilitation exercises. To account for additional treatment contact provided to participants in *I'm Whole*, UC+E will also receive 6 brief telephone calls with information regarding unrelated health topics (e.g., breast, colon, rectal, esophageal, skin and testicular cancer treatment and prevention).

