The waiver or alteration will not adversely affect the rights and welfare of the subjects, because the waiver will not affect the privacy rights and welfare of the potential participants as this knowledge will be gained from a medical records which can be accessed widely by VA researchers. The medical records information reviewed by the research staff that has already been shared with the patients and does not include undisclosed health information. The medical records examination will be limited to mental health diagnosis, coexisting medical conditions, hospitalization for psychiatric within the last 30 days. This information would have already been shared with the patient. Also, the data will not be used for any clinical purposes but only to determine eligibility for the current study.

Explain why the research could not practicably be conducted without the waiver and could not practicably be conducted without access to and use of the protected health information.

The research could not practicably be carried out without the waiver or alteration and without access to and use of the requested information, because conducting this initial medical chart investigation is essential to the research project. After experiencing a stroke, Veterans can experience a varying level of psychological distress and may have pre-existing psychological distress. Our program is not suited for participants with severe psychological distress. It would not be feasible to rely solely use the statements of the participant to gauge inclusion and exclusion criteria given patients with prior psychological distress may be more focused on the physical aspects of their stroke rather than their prior psychological symptoms. A greater focus on their physical changes may impact accurate recall of past information.

Describe how the research could not practicably be carried out without using the collected identifiable biospecimens in an identifiable format.

NA

Describe how an adequate plan exists in order to protect identifiers from improper use and disclosure.

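### Minor: the F2 invitation sentence negates only the first of its three items, so as written it invites Veterans whom F1 excludes

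*Combined protocol and SAP*

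**What the plan says.** **F1, Exclusion Criteria** (Phases II and III) has three items. The first is cognitive impairment on a brief screener. The second is a "documented diagnosis of psychotic disorder or schizophrenia". The third is "documented severe depression, anxiety (based on PHQ-8 or GAD-7 score of > 20), or hospitalization for psychiatric illness within the past 30 days".

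**F2, screening and recruitment paragraph** (also Phases II and III) turns the same three items into the rule for inviting Veterans after record review or baseline assessment. Item 1 reads "do not demonstrate or show evidence of a cognitive impairment, as evidenced by a score of >3 on a brief cognitive screener". Item 2 is having a recorded psychotic or schizophrenia diagnosis. Item 3 is scoring in the severe range, with the F1 cut-off, or having had a recent psychiatric admission. The sentence ends: "have a documented or self-reported hospitalization for psychiatric illness within the past 30 days, they will be invited to participate in the study".

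Earlier in that paragraph, records are checked "to see if they meet preliminary study inclusion/exclusion criteria (listed above". Later it says: "Participants who do not meet the criteria will be immediately notified of their ineligibility".

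**E2, Subjects**: "We will recruit male and female Veterans with mild to moderate symptoms of anxiety and depression". **J1, Waiver of Consent**: "Our program is not suited for participants with severe psychological distress". J1 also describes the eligibility chart review as looking for a psychotic or a bipolar diagnosis.

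The F2 sentence directly after the invitation gives those invited video instructions, the I'm Whole workbook and a first appointment with the clinician, and names no arm. F1 (Design) randomizes 15 Veterans to I'm Whole and 15 to UC+E. F1 and F2 both define UC+E as standard care plus 6 short telephone calls on unrelated health topics.

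**The concern.** The F2 sentence is the step at which eligibility is applied, not background text. As punctuated, it makes two of the three F1 exclusion items into conditions for entry. At stake is whether Veterans with a psychotic illness, severe distress or a recent psychiatric admission are invited to a program that the protocol itself describes as unsuited to severe distress. Staff can find the intended rule one section earlier, but a procedure should not need correcting by inference.

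The next sentence raises a smaller matter. Its subject is everyone invited, under a heading that covers the randomized phase, so its wording does not set the UC+E arm apart.

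**Working it through.** No figure in the plan depends on this wording, so there is none to reproduce. The check is a comparison of texts.

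**Where the negation sits.** In F2 the numeral 1 comes before *do not*, which places the negation inside item 1. Items 2 and 3 open with *have* and *score*, and the second half of item 3 opens with *have* again.

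| Condition | F1 | F2 as punctuated |
|---|---|---|
| Cognitive impairment | excludes | absence leads to invitation |
| Psychotic or schizophrenia diagnosis | excludes | presence leads to invitation |
| Severe PHQ-8 or GAD-7 score | excludes | presence leads to invitation |
| Recent psychiatric admission | excludes | presence leads to invitation |

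So 1 of the 3 numbered items is negated and 2 are not. Those 2 items hold three exclusion conditions.

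**What each reading admits.** Let A be cognitive impairment, B a psychotic or schizophrenia diagnosis, and C a severe score or a recent psychiatric admission. There are 2 × 2 × 2 = 8 possible profiles.

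| Rule | Profiles invited | Classified differently from F1 |
|---|---|---|
| F1: not A, not B, not C | 1 of 8 | – |
| F2, negation in item 1 only, all items required: not A, B, C | 1 of 8, a profile that F1 excludes | 2 of 8 |
| F2, negation in item 1 only, any item enough: not A, or B, or C | 8 − 1 = 7 of 8 | 7 − 1 = 6 of 8, all excluded by F1 |
| F2, negation carried through all items | 1 of 8, the same as F1 | 0 of 8 |

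The second and third rows are both given because F2 puts no connective between its numbered items. The profiles are logical combinations, not patient counts or proportions. Only the last reading reproduces F1.

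**Which reading is meant.** E2 limits recruitment to mild to moderate symptoms. F1 excludes by measured score. J1 puts severe distress outside the program. F2 itself refers back to the criteria already listed and tells those who fail them that they are ineligible. All four point to the last row.

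**Related wording.** F2 counts an admission that is documented or self-reported. In F1 the word *documented* opens the third item, and it is unclear whether it reaches as far as the hospitalization clause. A bipolar diagnosis appears in the J1 chart review but in neither the F1 list nor the F2 sentence.

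**The case against.** The best defence is grammatical. The subject of the F2 sentence is plural, so *have* and *score* have the same form whether they are affirmative or continue an understood *do not*. On that reading the numeral 1 is merely misplaced and F2 agrees with F1 throughout. The rest of the protocol settles the intent the same way. This stands, and it is why the point is minor. It does not make the sentence right, because the negation follows the numeral and the more natural reading is the wrong one.

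A reader might infer three stronger things, none of which the documents support:

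- *That the trial means to enrol Veterans with psychosis or severe distress, or that its sections disagree over the target population.* E2, F1, J1 and the cross-reference within F2 all say otherwise.
- *That F1 and F2 conflict on self-reported admissions.* If *documented* in F1 covers only depression and anxiety, F1 counts admissions from any source and agrees with F2. The wording is ambiguous, and a conflict is not shown.
- *That UC+E Veterans will receive I'm Whole materials and contaminate the comparison.* F1 and F2 define what each arm receives, the video sessions are described as the I'm Whole treatment, and J2 qualifies its video and telephone set-up step with an *if applicable*. The unnamed arm is an omission, and no dilution can be estimated from it.

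**Conclusion.** The F2 invitation sentence is wrong as written, and the error is minor. On its most natural reading, 2 of its 3 items reverse the F1 exclusions, and those items cover three exclusion conditions. The intended rule is not in real doubt, so this is a drafting error in an operative step and not a substantive conflict over who is studied. No sample-size, power or analysis figure is affected, and the documents give no count of patients at risk of being misclassified.

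The bipolar mismatch between J1 and F1 is one of content, and the two need reconciling. The documents do not show which is meant. The missing arm in the hand-out sentence is a secondary clarification that concerns the 15 of 30 Phase III Veterans planned for UC+E. F2 also does not say when randomization occurs, which is missing detail and not an inconsistency.

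The conclusion rests on the text alone. The telephone screening script that J1a places in section S is not in the material reviewed, so nothing is concluded about what staff would do in practice.

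**What to change.** 1. Replace the F2 invitation sentence with one that points to F1, for example: *Veterans who meet all inclusion criteria and none of the exclusion criteria in F1, on record review or at assessment, will be invited.* Use the same wording in the section S script.
2. State in both F1 and F2 whether a self-reported psychiatric admission counts.
3. Reconcile the diagnoses sought in the J1 chart review with the F1 exclusion list, so that both say the same about bipolar disorder.
4. In the next F2 sentence, name Phase II participants and Phase III participants allocated to I'm Whole as those who receive the workbook, video instructions and session booking, in line with the arm definitions in F1 and F2.

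The cost is about two sentences in F2, a matching phrase in F1 and in J1 as needed, and a check of the script. No staff, visits or procedures are added.
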